- To evaluate the effect of oral LAT8881, compared with placebo, on pain symptoms in subjects with NP, when measured by the short-form McGill Pain Questionnaire 2 (SF-MPQ-2)
- To evaluate the effect of oral LAT8881, compared with placebo, on symptoms in subjects with NP, when measured by the Neuropathic Pain Symptom Inventory (NPSI)
- To evaluate the effect of oral LAT8881, compared with placebo, on emotional functioning when measured by the Beck Depression Inventory-II (BDI-II)
- To evaluate the effect of oral LAT8881, compared with placebo, on overall health and quality of life in subjects with NP, when measured by the Patient Global Impression of Change (PGIC) scale
- To determine the change from baseline in paracetamol rescue medication use during oral LAT8881 administration, compared with placebo
- To evaluate the safety and tolerability of oral LAT8881 in NP after a single dose and after four weeks treatment
- To investigate the pharmacokinetics of twice daily oral LAT8881 in 15 subjects with NP after a single dose and after 4 weeks treatment with oral LAT8881

Exploratory

- To investigate the relationship between baseline subject characteristics, such as clinical diagnosis (PHN or DPN) and QST parameters, and the change in NPRS after oral LAT8881 treatment, compared with placebo
- To investigate the change from baseline on specified QST parameters after four weeks treatment with oral LAT8881,

compared with placebo

- To investigate the relationship between plasma LAT8881 concentrations and the change in mean pain score in subjects with NP
- To investigate the impact of variability in NPRS scores during the first baseline period on the difference between baseline and 4 week NPRS scores after LAT8881 or placebo

Endpoints Primary Endpoint

 Absolute change in mean pain score, using an 11 point NPRS, from baseline to the last week of each treatment period. Pain is recorded once daily in a subject diary, in the evening, and should reflect the subject's average pain over the last 24 hours

Baseline mean pain for each subject is defined as the mean of the last five available ratings of daily pain, recorded in each baseline period.

End of treatment mean pain for each subject is defined as the mean of the last five available ratings of daily pain, recorded in the last 7 days of each 4 week treatment period.

Secondary Endpoints

- Change in NPRS score at 0.5, 1, 2, 4 and 6 hours after the first dose

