On Day 14 (Visit 3), subjects will take their morning IMP dose and return to the clinic. Weight, vital signs, a targeted physical examination, concomitant medications and adverse events will be recorded. Subject compliance with medication and diary entries will be checked. Subjects will be reminded to continue their medication and to record daily entries into their diary.

On the morning of Day 28 (Visit 4, Last Day of First Treatment Period), subjects will not take their morning dose of IMP. They will make their morning diary entry and return to the clinic. At the clinic, weight, ECG, vital signs, a targeted physical examination, concomitant medications and adverse events will be recorded. Blood and urine samples will be taken for safety analysis. Subjects will complete assessments for Patient Reported Outcomes (interference scale of the short form BPI, SF-MPQ-2, NPSI, BDI-II, PGIC). In PK subjects, a pre-dose NPRS will be completed and a pre-dose blood sample will be taken for PK analysis.

Subjects (except PK and QST subjects) will then take their morning dose of IMP and leave the clinic. PK subjects will take their morning dose of IMP and stay for at least 6 hours. At scheduled times over this period, blood samples will be taken for PK analyses and NPRS assessments will be undertaken.

QST subjects will take their morning dose of IMP and will have specified QST parameters assessed 2 hours after this dose. An appointment for a QST assessment will be scheduled within seven days of the first dose of the second treatment period.

All subjects will take their second Day 28 IMP dose in the evening.

Washout (Days 29 to 42)

Subjects will be asked to discontinue their IMP after their evening dose on Day 28. Daily diary NPRS entries should be continued.

Second Baseline Period (Days 43 to 49)

Subjects will continue daily diary entries and will not take any IMP over Days 43 to 49 inclusive (second baseline).

Second Treatment Period (Days 50-77)

Subjects will return to the unit on Day 50 (Visit 5) with their diary completed from Days 29 to 49 inclusive. QST subjects will have a pre-dose QST assessment, if not completed within the previous 7 days.

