2.1 Screening, First Baseline Period, First Treatment Period and Washout

	Screening	Screening Stage 2 (First					
	Stage 1 Baseline)		Firs	t Treatment Pe	eriod	Washout	
Visit No	1		2 3 4		4		
Study Day	-28 to -8	-7 to -1	1	14 ± 1	28 ± 1	29 (+/-1) to 42 (+/-1)	
Written informed consent	Х						
Eligibility assessment	Х						
Pain diary training	Х						
Confirmation of eligibility			Х				
Enrolment			Х				
Randomisation			Х				
Medical history, demographics	Х						
Height, ¹ weight	Х		Х	Х	Х		
PD-Q	Х		Χ				
12 lead ECG	Х		X ²		X ²		
Vital signs	Х		X^3	Х	Х		
Physical examination ⁴	Х		X ⁵	X ⁵	X ⁵		
Concomitant medications	Х		Χ	Х	Х		
Clinical laboratory safety testing ⁶	Х		X ^{2,7}		X ²		
Pregnancy test ⁸	X ⁹		X ¹⁰				
QST sensory phenotype assessment ¹¹			X ¹²		Х		
IMP administration			X ¹³	Х	X ¹³		
Adverse event assessment	X ¹⁴	X ¹⁴	Χ	Х	Х		
Blood sampling for PK analysis ¹⁵			X ¹⁶		X ¹⁶		
Daily NPRS ratings ¹⁷		Х	X ¹⁸	Х	X ¹⁸	Х	
Short form BPI assessment			Х		Х		
Short form McGill questionnaire 2			Χ		Х		
Neuropathic Pain Symptom Inventory			Χ		Х		
Beck Depression Index-II			Χ		Х		
PGIC					Х		

- 1 Height measured only at screening
- 2 Pre-dose
- 3 Pre-dose and 0.5 hours post-dose
- 4 Includes assessment of area of pain
- 5 Targeted physical examination
- 6 Haematology, clinical chemistry, urinalysis
- 7 Results of clinical laboratory tests not required prior to dosing
- 8 Females of child bearing potential only
- 9 Blood pregnancy test
- 10 Urine pregnancy test
- 11 QST subjects only
- 12 QST to be assessed pre-dose, within 7 days of the first dose
- 13 Supervised administration
- 14 SAEs only (UK subjects only)
- 15 PK subjects only
- 16 Pre-dose and up to 6 hours post-dose
- 17 Each evening, throughout baseline, treatment and washout periods
- 18 Additional ratings pre-dose and up to 6 hours post-dose in PK subjects

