2.2 Second Baseline Period, Second Treatment Period and Follow Up

	Second Baseline Period	Second Treatment Period			End of Study
Visit No		5	6	7	8
Study Day	43 to 49	50 ± 1	63 ± 1	77 ± 1	91 ± 2
Weight		Х	Х	Х	Х
12 lead ECG		X ¹⁹		X ¹⁹	
Vital signs		X ²⁰	Х	Х	Х
Physical examination ²¹		X ²²	X ²²	X ²²	X ²²
Concomitant medications		Х	Х	Х	Х
Clinical laboratory safety testing ²³		X ^{19,24}		X ¹⁹	Х
QST sensory phenotype assessment ²⁵		X ²⁶		Х	
IMP administration		X ²⁷	Х	X ²⁷	
Adverse event assessment		Х	Х	Х	Х
Blood sampling for PK analysis ²⁸		X ²⁹		X ²⁹	
Daily NPRS ratings ³⁰	Х	X ³¹	Х	X ³¹	
Short form BPI assessment		Х		Х	
Short form McGill questionnaire 2		Х		Х	
Neuropathic Pain Symptom Inventory		Х		Х	
Beck Depression Index-II		Х		Х	
PGIC				Х	

¹⁹ Pre-dose

²⁰ Pre-dose and 0.5 hours post-dose

²¹ Includes assessment of area of pain

²² Targeted physical examination

²³ Haematology, clinical chemistry, urinalysis

²⁴ Results of clinical laboratory tests not required prior to dosing

²⁵ QST subjects only

²⁶ QST to be assessed pre-dose, within 7 days of the first dose of this treatment period

²⁷ Supervised administration

²⁸ PK subjects only

²⁹ Pre-dose and up to 6 hours post-dose

³⁰ Each evening throughout baseline and treatment periods

³¹ Additional ratings pre-dose and up to 6 hours post-dose in PK subjects

3. Introduction and background information

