Subjects will be reminded to continue their medication and to continue to record daily NPRS entries into their diary. They will be asked to return on Day 28 with their medication bottle, but without taking their morning dose of IMP. They will also be reminded not to take paracetamol within 4 hours of the next clinic visit.

8.3.3 Day 28 (± 1), Visit 4

On the morning of Day 28 (Visit 4, Last Day of First Treatment Period), subjects will not take their morning dose of IMP. They will return to the clinic with their medication bottle.

The following assessments will be undertaken:

- Weight
- ECG
- Vital signs
- Targeted physical examination
- Concomitant medications
- Blood and urine samples for safety analysis (haematology, clinical chemistry, urinalysis)
- Adverse events
- · Compliance with medication
- Compliance with diary entries

Subjects will also complete assessments for Patient Reported Outcomes:

- Interference scale of the short form BPI
- SF-MPQ-2
- NPSI
- BDI-II
- PGIC

Subjects (except PK and QST subjects) will take their morning dose of IMP and leave the clinic. They will take their Day 28 evening dose and then discontinue treatment until their next visit on Day 50. They will be asked to continue daily NPRS diary entries, and to return to the unit on Day 50 with their medication bottle. They will also be reminded not to take paracetamol within 4 hours of the next clinic visit.

In PK subjects, a pre-dose NPRS will be completed (maximum one hour before dosing) and a pre-dose blood sample will be taken for PK analysis. PK subjects will take their morning dose of IMP and remain in

the clinic for at least 6 hours. At scheduled times (2, 5, 15, 30, 60 minutes, 2, 4 and 6 hours after IMP dosing), blood samples will be taken for PK analysis. NPRS will be monitored at 0.5, 1, 2, 4 and 6 hours. Subjects will then leave the clinic. They will take their Day 28 evening dose and then discontinue treatment until their next visit on Day 50. They will be asked to continue daily diary entries, and to return to the unit on Day 50 with their medication bottle. They will also be reminded not to take paracetamol within 4 hours of the next clinic visit.

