9.1 Primary endpoint

Absolute change in mean pain score, using an 11 point NPRS, from baseline to the last week of
each treatment period. Pain is recorded once daily in a subject diary in the evening, and should
reflect the subject's average pain over the last 24 hours

Baseline mean pain for each subject is defined as the mean of the last five available ratings of daily pain, recorded in each baseline period.

End of treatment mean pain for each subject is defined as the mean of the last five available ratings of daily pain, recorded in the last 7 days of each 4 week treatment period.

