10.5 Efficacy assessments

10.5.1 Pain intensity

10.5.1.1 NPRS

The NPRS is an 11 point scale which grades pain from 0 (no pain) to 10 (worst pain imaginable). It is a recommended core outcome for the assessment of pain intensity in clinical trials of chronic pain treatments.¹⁶

Subjects will be asked to rate the intensity of their average pain over the previous 24 hours in a diary. Entries should be made at the same time each evening.

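### The synopsis asks for a morning diary entry on Days 28 and 77, which contradicts the once-daily evening rating behind the primary endpoint; the SAP has no rule to handle such an entry (minor consistency error)

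*Protocol*

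**What the plan says.** In the Protocol synopsis, the study procedures for Day 28 (Visit 4) and Day 77 (Visit 7) have subjects withhold the morning dose, and then: "They will make their morning diary entry and return to the clinic". The sentence is the same for both days.

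The other places that give a diary time all say evening:

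- Synopsis, Primary Endpoint: pain is "recorded once daily in a subject diary, in the evening".
- Protocol 9.1: "Pain is recorded once daily in a subject diary in the evening". The end-of-treatment mean uses the last five available ratings "recorded in the last 7 days of each 4 week treatment period". SAP 7.1 repeats this definition.
- Protocol 10.5.1.1: "Entries should be made at the same time each evening". SAP 15.3.1 repeats it.
- Schedule 2.1, footnote 17: "Each evening, throughout baseline, treatment and washout periods". Schedule 2.2, footnote 30: "Each evening throughout baseline and treatment periods". SAP 5.1 and 5.2 carry the same footnotes.

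The detailed Day 28 procedure (Protocol 8.3.3) says only: "They will return to the clinic with their medication bottle". Section 8.6.3 is equivalent for Day 77. Neither mentions a morning diary entry.

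SAP 10.15.1 averages the last five available daily ratings in each 7-day period and sets the mean to missing if there are fewer than five. It does not mention time of day or two entries on one day. SAP 10.3 defines week 4 as Days 22-28 in period 1 and Days 70-76 in period 2.

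**The concern.** Days 28 and 77 are the last days of their treatment periods, and a rule that takes the latest five ratings reaches for them first. The Protocol gives two incompatible instructions for those days. It does not say whether a morning entry would replace the evening rating or add to it.

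If it replaces the evening rating, one component of the end-of-treatment mean is taken at a different time of day from the rest, and from the baseline ratings. If it is added, one day counts twice and the five ratings span four days. In a week with only four rated days, the extra entry would also bring the count to five, so a mean that SAP 10.15.1 sets to missing would be calculated. Sites working from the synopsis and sites working from Section 8 could therefore collect the primary endpoint differently.

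**Working it through.** **1. The plan's own figure.** Inputs (synopsis, Statistical Analysis; Protocol 13.2): difference 1, SD of change 2, within-subject correlation 0.5, two-sided 5%, power 90%, dropout 20%.

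- SD of the within-subject difference = √(2 × 2² × (1 − 0.5)) = 2.0.
- Normal approximation: n = (2.0 × (1.960 + 1.282) / 1)² = 42.03, so 43.
- Noncentral t with n − 1 degrees of freedom: power 90.0% at n = 44.
- 44 / (1 − 0.20) = 55.

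The stated 44 and 55 reproduce. This point does not dispute them.

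**2. Which periods are exposed.** Period 2 starts on Day 50, so Day 77 is its day 77 − 50 + 1 = 28.

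| Rule | Period 1 | Period 2 | Last day included? |
|---|---|---|---|
| Endpoint definition (last 7 days) | Days 22-28 | Days 71-77 | Yes, both |
| SAP 10.3, week 4 | Days 22-28 | Days 70-76 | Period 1 only |

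The one-day shift arises because SAP 10.3 gives week 2 of period 2 as Days 57-62, which is six days. Under the SAP windows no Day 77 entry, morning or evening, enters the mean.

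**3. Replacement.** One rating of five has weight 1/5 = 20%. The documents give no morning-evening difference, so a range is assumed:

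| Assumed difference (points) | Shift in end-of-treatment mean (difference / 5) |
|---|---|
| 0.5 | 0.1 |
| 1 | 0.2 |
| 2 | 0.4 |

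This is a shift in one subject's mean in one period, not in the treatment contrast. If the morning entry came 12 hours after the previous evening's entry (also an assumption), half of its 24-hour recall (12/24) would repeat that entry.

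**4. Effect on the contrast.**

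- A shift that is equal on both treatments and present in both periods cancels in the LAT8881-placebo difference.
- A shift confined to period 1 falls about equally on both treatments if the two sequences are of about equal size, and the period term in the model (SAP 11.6.1.2) largely absorbs it.
- The contrast moves only if the morning rating carries a different share of the treatment effect. With share s, the contrast is 1 − (1 − s)/5. Taking every subject and both periods as affected, with n = 44 and an SD of 2.0:

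| Share s | Contrast | Power |
|---|---|---|
| 100% | 1.00 | 90.0% |
| 50% | 0.90 | 83.1% |
| 0% | 0.80 | 73.7% |

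The 0% row is an implausible extreme, because the rating recalls the previous 24 hours.

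**5. Duplication.** With a full diary, the last five entries in period 1 become Days 25, 26, 27, 28 (morning) and 28 (evening). Day 24 drops out and Day 28 has weight 2/5 = 40%. Let r be the day-to-day correlation (assumed) and take the two Day 28 entries as identical. In units of the daily variance, the variance of the mean goes from r + (1 − r)/5 to r + (1 − r)(3 × 0.04 + 0.16):

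- r = 0.3: 0.44 to 0.50.
- r = 0.7: 0.76 to 0.78.

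**The case against.** The strongest reply is that the design is not in doubt. The endpoint definition, both schedules, Section 10.5.1.1, the detailed procedures and the SAP all keep the evening rating, and Section 5.1 refers to Section 8 for procedural detail. Nothing cancels the evening rating on Days 28 or 77. Counting two entries for one day would go against a measure defined as once daily. The disputed sentence does not even say that the entry is an NPRS rating, although that is the natural reading. All of this stands, and it limits the point to a consistency error.

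A reader might infer that the final rating is mistimed or duplicated for every subject in both periods, and that the treatment comparison is biased. The documents do not support this. It happens only where a site follows the synopsis sentence, and under the SAP windows Day 77 does not enter the mean at all. The 20% and 40% are weights within a mean and do not measure bias.

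The reply does not remove the contradiction. The sentence is an operational instruction, given twice. The replacement reading is not far-fetched. The Day 28 and Day 77 evening entries fall after that day's visit. Section 8.6 has subjects return on Day 50 with the diary for Days 29-49, and Section 8.7.1 lists no diary review. The Protocol's amendment appendix notes that the diary is not electronic, so the documents describe no lockout that would enforce one evening entry. The SAP has no rule to sort out the data afterwards.

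**Conclusion.** The contradiction is real and concerns how the primary endpoint is collected. At a site that follows the synopsis, one of the five ratings may be a morning rating, or the last day may supply two of the five. This is confined to period 1 under the SAP windows and extends to both periods under the endpoint definition.

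The consequence for the LAT8881-placebo contrast is probably small, and no bias is shown. That judgement assumes that any morning-evening difference is similar on the two treatments and that the sequences are of about equal size. The documents give no data on the first and do not state the allocation ratio. The sample size is unaffected. This is a minor consistency error, worth correcting because the correction is specific and nearly free.

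**What to change.** 1. Protocol synopsis, Day 28 and Day 77: delete the clause about a morning diary entry from both sentences, so that they agree with the evening rating and with Sections 8.3.3 and 8.6.3.
2. SAP 10.15.1: state that only evening diary ratings, at most one per calendar day, enter the baseline and weekly means, and that any morning diary entry is listed only.
3. SAP 10.3: reconcile the period 2 week-4 window (Days 70-76) with the endpoint definition, which includes Day 77. Items 1 and 2 do not resolve this.

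The cost is wording in two synopsis sentences and two SAP sections, to be settled before database lock. Subjects have no added burden and the sample size does not change. One consequence should be accepted openly: a subject whose only entry on the last day was made in the morning loses that rating, and the mean then needs five evening ratings from the other six days of the window.

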2.1 Screening, First Baseline Period, First Treatment Period and Washout

	Screening	Screening Stage 2 (First					
	Stage 1 Baseline)		Firs	t Treatment Pe	eriod	Washout	
Visit No	1		2 3 4		4		
Study Day	-28 to -8	-7 to -1	1	14 ± 1	28 ± 1	29 (+/-1) to 42 (+/-1)	
Written informed consent	Х						
Eligibility assessment	Х						
Pain diary training	Х						
Confirmation of eligibility			Х				
Enrolment			Х				
Randomisation			Х				
Medical history, demographics	Х						
Height, ¹ weight	Х		Х	Х	Х		
PD-Q	Х		Χ				
12 lead ECG	Х		X ²		X ²		
Vital signs	Х		X^3	Х	Х		
Physical examination ⁴	Х		X ⁵	X ⁵	X ⁵		
Concomitant medications	Х		Χ	Х	Х		
Clinical laboratory safety testing ⁶	Х		X ^{2,7}		X ²		
Pregnancy test ⁸	X ⁹		X ¹⁰				
QST sensory phenotype assessment ¹¹			X ¹²		Х		
IMP administration			X ¹³	Х	X ¹³		
Adverse event assessment	X ¹⁴	X ¹⁴	Χ	Х	Х		
Blood sampling for PK analysis ¹⁵			X ¹⁶		X ¹⁶		
Daily NPRS ratings ¹⁷		Х	X ¹⁸	Х	X ¹⁸	Х	
Short form BPI assessment			Х		Х		
Short form McGill questionnaire 2			Χ		Х		
Neuropathic Pain Symptom Inventory			Χ		Х		
Beck Depression Index-II			Χ		Х		
PGIC					Х		

- 1 Height measured only at screening
- 2 Pre-dose
- 3 Pre-dose and 0.5 hours post-dose
- 4 Includes assessment of area of pain
- 5 Targeted physical examination
- 6 Haematology, clinical chemistry, urinalysis
- 7 Results of clinical laboratory tests not required prior to dosing
- 8 Females of child bearing potential only
- 9 Blood pregnancy test
- 10 Urine pregnancy test
- 11 QST subjects only
- 12 QST to be assessed pre-dose, within 7 days of the first dose
- 13 Supervised administration
- 14 SAEs only (UK subjects only)
- 15 PK subjects only
- 16 Pre-dose and up to 6 hours post-dose
- 17 Each evening, throughout baseline, treatment and washout periods
- 18 Additional ratings pre-dose and up to 6 hours post-dose in PK subjects

2.2 Second Baseline Period, Second Treatment Period and Follow Up

	Second Baseline Period	Second Treatment Period			End of Study
Visit No		5	6	7	8
Study Day	43 to 49	50 ± 1	63 ± 1	77 ± 1	91 ± 2
Weight		Х	Х	Х	Х
12 lead ECG		X ¹⁹		X ¹⁹	
Vital signs		X ²⁰	Х	Х	Х
Physical examination ²¹		X ²²	X ²²	X ²²	X ²²
Concomitant medications		Х	Х	Х	Х
Clinical laboratory safety testing ²³		X ^{19,24}		X ¹⁹	Х
QST sensory phenotype assessment ²⁵		X ²⁶		Х	
IMP administration		X ²⁷	Х	X ²⁷	
Adverse event assessment		Х	Х	Х	Х
Blood sampling for PK analysis ²⁸		X ²⁹		X ²⁹	
Daily NPRS ratings ³⁰	Х	X ³¹	Х	X ³¹	
Short form BPI assessment		Х		Х	
Short form McGill questionnaire 2		Х		Х	
Neuropathic Pain Symptom Inventory		Х		Х	
Beck Depression Index-II		Х		Х	
PGIC				Х	

¹⁹ Pre-dose

²⁰ Pre-dose and 0.5 hours post-dose

²¹ Includes assessment of area of pain

²² Targeted physical examination

²³ Haematology, clinical chemistry, urinalysis

²⁴ Results of clinical laboratory tests not required prior to dosing

²⁵ QST subjects only

²⁶ QST to be assessed pre-dose, within 7 days of the first dose of this treatment period

²⁷ Supervised administration

²⁸ PK subjects only

²⁹ Pre-dose and up to 6 hours post-dose

³⁰ Each evening throughout baseline and treatment periods

³¹ Additional ratings pre-dose and up to 6 hours post-dose in PK subjects

3. Introduction and background information

3.1 Neuropathic pain

Neuropathic pain (NP) is defined as pain caused by a lesion or disease of the somatosensory nervous system.² The damage may be located either centrally or peripherally. Examples of central neuropathic pain include pain in multiple sclerosis or Parkinson's disease and pain after a stroke; examples of peripheral neuropathic pain include painful diabetic neuropathy, phantom limb pain, post-herpetic neuralgia, chemotherapy induced polyneuropathy, and trigeminal neuralgia.

[figure not shown]
The symptoms of peripheral neuropathic pain vary, depending upon the type of nerves that are damaged. Typical descriptions of the pain include shooting, stabbing, electric shock, burning, tingling, tight, numbness, prickling, itching and a sensation of pins and needles. Symptoms may also include allodynia, hyperalgesia, anaesthesia dolorosa, with sensory gain or loss. The impact of neuropathic pain on both the individual and on society is substantial. In addition to the morbidity associated with the pain itself, patients with neuropathic pain have a decreased quality of life, increased use of healthcare resources, increased absenteeism and decreased productivity at work.

The development of validated questionnaires for neuropathic pain has enabled better assessment of its prevalence in the general population. A recent systematic review of epidemiological studies of neuropathic pain estimated that the prevalence of pain with neuropathic characteristics ranged from 7-10%.³ This is likely to increase as the population ages, when there will be an increased incidence of risk factors for neuropathic pain, such as diabetes, cancer and cancer chemotherapy.

The treatment of neuropathic pain is challenging as it is generally not possible to alleviate the cause of the pain. Rather, therapy focuses on treating the symptoms. Non-pharmacological treatments, such as physical exercise, cognitive behavioural therapy and meditation have been proposed but there is only weak evidence for the efficacy of such approaches.⁴ Pharmacological therapy is the mainstay of treatment. A recent review of 229 randomised double-blind studies of oral and topical pharmacotherapy for neuropathic pain by the Neuropathic Pain Special Interest Group (NeuPSIG) of the International Association for the Study of Pain (IASP) recommended gabapentin, gabapentin extended release/enacarbil, pregabalin, duloxetine, venlafaxine and tricyclic antidepressants as first line therapy.⁵ However, it was found that outcomes with these agents were generally only modest, with 4 to 10 patients requiring active treatment for a 50% reduction in pain, compared with placebo treatment. Moreover, many of these therapies have side effects, such as somnolence, dizziness, motor imbalance and cognitive impairment, which restrict a patient's activities and diminish their quality of life.⁶

There is clearly an unmet need for more effective therapies to treat neuropathic pain. LAT8881 has a different mechanism of action to current therapies and has shown promising activity in animal models of neuropathic pain. It also has a good preclinical and clinical safety record. This is the first clinical study to investigate this compound in neuropathic pain.

